14.7. Other Exploratory Analysis

Digital Device Performance by amount of digital device use

Subjective responses to digital device items will be grouped as: $aval=1$ is a subject responds' 'Excellent' or 'Very Good', $aval=2$ is a subject responds' 'Good' and $aval=3$ if a subject

Clinical Study Protocol

Johnson & Johnson Vision Care, Inc.

responds' 'Fair' or 'Poor'. Amount of digital device use is collected by self-report at the follow-up visit: the subject is asked their average number of hours of digital device use on the days between visits that they wore the study lenses. Subjects with digital device use below the 50th percentile of the distribution of digital device use for all subjects in the study will be classified as grp1 (lower digital device usage), and subjects with digital device use above the 50th percentile will be classified as grp2 (higher digital device usage). Digital device items will be analyzed separately using a generalized linear mixed model with a multinomial distribution and the cumulative logit as the link function. Sequence of lens wear, period, lens type, group (grp 1 and grp 2) and the interaction between lens type and group will be included in each model as fixed effects. Site and subject nested within site will be included as a random effect. Errors between measurements within the same subject across study periods will be modeled using an unstructured covariance (UN) structure. Comparisons between O1D and P1 will be carried for each group separately (grp 1 and grp 2) out using 1-sided 97.5% confidence intervals (CIs) constructed for the odds ratio (O1D over P1). Non-inferiority of O1D relative to P1 will be concluded if the lower limit of the 97.5% CI is above 0.67 (using 10% as non-inferiority margin and assuming a reference proportion of 0.5) .

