3.2. Inclusion Criteria

Potential subjects must satisfy all of the following criteria to be enrolled in the study:

Inclusion Criteria following Screening

The subject must:

1. Read, understand, and sign the STATEMENT OF INFORMED CONSENT and receive a fully executed copy of the form.
2. Appear able and willing to adhere to the instructions set forth in this clinical protocol.
3. Be between 18 and 40 (inclusive) years of age at the time of screening.
4. By self-report, habitually wear soft spherical contact lenses in both eyes in a daily disposable wear modality. Habitual wear is defined as a minimum of 8 hours of wear per day, for a minimum of 4 days per week during the past 4 weeks.
5. By self-report, typically uses computer screens and other digital devices (phones, tablets) at least 30 hours per week.

Inclusion Criteria at Baseline Evaluation

6. The vertex-corrected best spherical distance refraction (rounded to nearest 0.25 D) must be between -1.00 and -4.00 DS (inclusive) in each eye.
7. The magnitude of the cylinder component of the subject's distance refraction must be 1.00 DC or less.
8. The subject must have best corrected visual acuity of 20/25 or better in each eye.

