7.2. Detailed Study Procedures

VISIT 1

The subjects must present to Visit 1 wearing spectacles, having not worn contact lenses on the day of the visit.

Visit 1: Screening			
Step	Procedure	Details	
1.1	Statement of Informed Consent	Each subject must read, understand, and sign the Statement of Informed Consent before being enrolled into the study. The Principal Investigator or his/her designee conducting the informed consent discussion must also sign the consent form. Note: The subject must be provided a signed copy of this document.	
1.2	Demographics	Record the subject's year of birth, age, gender, race and ethnicity.	
1.3	Medical History and Concomitant Medications	Record the subject's medical history and concomitant medications.	

Clinical Study Protocol
Johnson & Johnson Vision Care, Inc.

Visit 1: Screening			
Step	Procedure	Details	
1.4	Habitual Contact Lens Information	Questions regarding the subject's habitual lens type and parameters.	
1.5	Habitual Contact Lens Wear Schedule	Record the duration of wearing this contact lens type and power (number of years and months). During the past 4 weeks, what is the minimum number of days per week that the subject has worn their lenses for at least 8 hours.	
1.6	Typical usage of digital devices	In a typical week, how many hours does the subject use computer screens and other digital devices (phones, tablets)?	
1.7	Eligibility after Screening	All responses to Screening Inclusion Criteria questions must be answered "yes" and all responses to Exclusion Criteria must be answered "no" for the subject to be considered eligible. If subject is deemed to be ineligible after screening, proceed to Final Evaluation and complete Subject Disposition. Refraction and Biomicroscopy forms do not need to be completed as part of Final Evaluation.	

Visit 1: Baseline			
Step	Procedure	Details	
1.8	Subject Reported Ocular Symptoms	Subjects will respond to a verbal open-ended symptoms questionnaire.	
1.9	Entrance Visual Acuity	Record the distance Snellen visual acuity (OD, OS, OU) to the nearest letter with their habitual spectacle correction in place. Subjects must read the smallest line until at least 50% of the letters are read incorrectly.	
1.10	Keratometry/SimK	Record the keratometry or SimK readings OD and OS in diopters.	

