2.4	Digital Device usage	On the days between visits (ie. not including the day of fitting and day of follow-up) when contact lenses were worn, what was the average amount of time per day spent using computer screens and other digital devices (phones, tablets)?
2.5	Compliance	Confirm compliance with the prescribed wear schedule.
2.6	Entrance Visual Acuity	Record the distance Snellen visual acuity (OD, OS, OU) to the nearest letter with the study contact lenses in place. Subjects must read the smallest line until at least 50% of the letters are read incorrectly.
2.7	PRO questionnaire	The subject will respond to the Follow-Up PRO (MRD) Questionnaire.
2.8	Lens Fit Assessment	
Evaluate lens centration, movement on blink, and push-up test for each eye.
 
An unacceptable fit is defined by one or more of the following criteria:
 
 • limbal exposure at primary gaze or with extreme eye movement • edge lift • excessive movement with blink in primary gaze • insufficient movement with blink in upgaze • insufficient movement in push-up test 
Note: if lens fit is unacceptable for either eye, the subject will be discontinued from the study.

2.9	Lens Removal	Have the subject remove the study lenses. Temporarily store the worn lenses until Biomicroscopy has been completed. If no adverse event or PQC was recorded, the worn lenses may be discarded.

Clinical Study Protocol
Johnson & Johnson Vision Care, Inc.

Visit 2: Treatment 1 Follow-up		
Step	Procedure	Details
2.10	Slit Lamp Biomicroscopy	
FDA Slit Lamp Classification Scale will be used to grade the findings.
 
If the clearance of the fluorescein needs to be expedited, preservative-free rewetting drops or saline may be instilled.

2.11	Exit Visual Acuity	
Record the distance Snellen visual acuity (OD, OS, OU) to the nearest letter with their habitual spectacle correction in place.
 
Subjects must read the smallest line until at least 50% of the letters are read incorrectly.

2.12	Schedule next visit	
The next scheduled visit is 6 to 8 days after Visit 2.

2.13	Subject Instructions	
Instruct the Subject on the following:
 
 • Subjects may wear their habitual spectacles or contact lenses during the washout period. • The subject must wear their spectacles to the next scheduled visit, having not worn their contact lenses on the day of the visit.

VISIT 3

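### The exploratory device-use split rests on hours reported while wearing the study lenses, with no rule for which report classifies a subject or where values at the median go

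*Combined protocol and SAP*

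**What the plan says.** Section 14.7 (Other Exploratory Analysis) takes its grouping variable from the study period: "Amount of digital device use is collected by self-report at the follow-up visit". One group holds subjects "below the 50th percentile of the distribution of digital device use for all subjects in the study will be classified as grp1". For the other, "subjects with digital device use above the 50th percentile will be classified as grp2". The model for each device item then has group as a fixed effect, and "the interaction between lens type and group will be included in each model as fixed effects". Non-inferiority is concluded separately in each group against an odds ratio of 0.67.

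The detailed procedures in Section 7.2 ask the device-hours question twice, at Visit 2 (step 2.4) and Visit 4 (step 4.4). Each time it covers the days on which lenses were worn since the fitting: "what was the average amount of time per day spent using computer screens and other digital devices (phones, tablets". A completer therefore has one value for each lens.

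A separate measure is taken at Visit 1 (step 1.6), before randomisation at step 1.16: "In a typical week, how many hours does the subject use computer screens and other digital devices (phones, tablets". Section 14.7 does not use it. Inclusion criterion 5 also concerns typical use, since it admits a person who "typically uses computer screens and other digital devices (phones, tablets) at least 30 hours per week".

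Under Section 14.4, exploratory hypotheses are tested only if all primary and secondary group 2 hypotheses are met.

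**The concern.** Three features of the split need attention.

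- **Timing.** The grouping variable is observed after randomisation, on the lenses being compared. The outcomes are comfort and dryness during device use. A lens that is less comfortable at a screen could shorten screen time, so the lens might help decide which group a subject or record falls in.
- **Undefined derivation.** Each completer has two reports, while Section 14.7 refers to the follow-up visit in the singular. Two programmers could build different groups from the same data, and the choice could be made after results are seen.
- **Open boundary.** One rule is strictly below and the other strictly above the median. A value equal to the median has no group. Section 14.9 does not help, because such a value is not missing.

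At stake is the one question this analysis asks: whether the lens comparison differs between lighter and heavier device users. The plan attaches a formal conclusion to each group.

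**Working it through.** The documents give no figure for this split, so there is none to reproduce. The check sets out the possible readings and then illustrates their size.

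**Readings that fit the text**

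- *One visit only (Visit 2 or Visit 4).* One label per subject and no switching. The label reflects use on whichever lens was worn in that period, so it could depend on the assigned sequence.
- *Mean of both visits.* One label per subject, no switching, and both lens ratings stay in the same group. The label can still reflect reactions to the lenses.
- *Each period's own value.* Two labels per subject. A subject who changes group contributes one lens to each group, so part of the within-group comparison is between different people.

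On all three readings the variable is measured after randomisation and values at the median are unassigned. Switching arises only on the third.

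**Assumed inputs (none is in the documents):** normally distributed daily hours with mean about 7, SD 2 to 3 h, between-period correlation r of 0.5 to 0.9, answers rounded to 1 h or 0.5 h, and a single cut at the median (pooled over both reports when periods are used separately). Simulations used 500 replicates per setting, with 60 and 300 subjects.

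**Ties, single reports.** With rounding step w, the share at the median is about 2Φ(w/(2·SD)) − 1.

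- w = 1 h: SD 2 gives 2Φ(0.25) − 1 = 19.7%; SD 3 gives 2Φ(0.167) − 1 = 13.2%. Simulation: 13–20% of records.
- w = 0.5 h: SD 2 gives 2Φ(0.125) − 1 = 9.9%; SD 3 gives 2Φ(0.083) − 1 = 6.6%. Simulation: 7–10% of records.
- Used period by period, 12–35% of subjects have at least one unclassified period in simulation.

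**Ties, mean of two reports.** The mean has SD·√((1 + r)/2) and a rounding step of w/2.

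- SD 2, r = 0.5, w = 1: SD of the mean is 1.732, and 2Φ(0.25/1.732) − 1 = 11.5%.
- SD 3, r = 0.9, w = 0.5: SD of the mean is 2.924, and 2Φ(0.125/2.924) − 1 = 3.4%.
- Simulation over all settings: 3–11% of subjects.

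**Switching, period-by-period reading only.** For unrounded bivariate normal values, the probability of falling on opposite sides of the median is arccos(r)/π: 33% at r = 0.5, 25% at 0.7, 20% at 0.8 and 14% at 0.9. With rounding, some of these subjects tie instead of switching. The simulated range is then 2% (whole hours, SD 2, r = 0.9) to 28% (half hours, SD 3, r = 0.5).

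**With the group fixed at baseline.** One value per subject and a rule that includes the median give 0% unclassified and 0% switching by construction, among subjects with a recorded value.

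**The case against.** A reader might infer that subjects do switch groups between lenses and that the within-subject pairing is lost. The documents do not support that. Section 14.7 classifies subjects, which reads most naturally as one label each. It neither states nor excludes a period-specific label. Even on that reading pairing would be weakened and not lost, because most subjects would keep one group under the illustrative inputs and the model retains a subject random effect.

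A reader might also infer that the result is biased. That too goes further than the text: nothing in the documents shows that either lens changes device use, and no direction or size can be given. It is a risk.

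There is a reasonable case for the on-study variable. Section 2.2 names it as the exploratory endpoint, and it covers the period in which the device items are rated. Typical weekly use is a different quantity, and the 30-hour entry floor cuts off its lower range. Section 14.1 also defers detail to a stand-alone SAP, where tie handling and visit selection might be settled.

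What stands: naming one on-study value and assigning ties would close both definitional gaps, but the grouping variable would still be measured after randomisation. The choice of variable is therefore more than a missing programming detail.

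**Conclusion.** The point holds in a limited form. The split uses hours reported after randomisation on the study lenses, does not say which of two reports classifies a subject, and leaves values equal to the median without a group. Because comfort could affect device use, the lens comparison within each group may be biased. Group switching is possible on one reading only.

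The sizes are illustrations: 3–11% of subjects tied if the reports are averaged, 7–20% of records tied if they are used separately, and 2–28% of subjects switching if the rule is applied by period. They rest entirely on the assumed SD, rounding and correlation.

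Severity is low. No primary or secondary conclusion, sample size or interim decision depends on this analysis.

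**What to change.** Define the group once per subject from the typical weekly device hours recorded at step 1.6: grp1 at or below the median, grp2 above. Alternatively, keep baseline hours continuous and interact them with lens type, which avoids a cut-point.

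Retain on-study use as a supportive analysis, reduced to one value per subject (for example the mean of the Visit 2 and Visit 4 reports), with ties assigned by the same closed rule.

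The cost is wording in Section 14.7 and the SAP; the data are already collected. There are three downsides. Typical weekly use stands in for use on the lenses, its range is truncated at 30 hours per week, and ties may make the two groups unequal in size.

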14.8. Interim Analysis

This is a two-phase adaptive approach utilizing stopping rules. Approximately 65 subject will be enrolled in Phase with a target of 60 to complete. An interim analysis will be performed after all subjects have completed Phase I on primary endpoints only. Data from Phase I will be utilized to calculate the number of subjects required to complete Phase II to achieve all primary hypotheses with at least 80% power. However, maximum enrollment for Phase II can be no more than 300 subjects (based on resources and study timing). After reviewing the results from the interim analysis, the study may be stopped prior to beginning enrollment for Phase II for one of the following reasons:

1. Lack of efficacy with respect to primary endpoints (results are inconclusive)
2. Required sample size too large to achieve primary endpoints

Full details regarding the planned interim analysis are located in Section 14.5 above. Information about how the sample size calculations for Phase II will be conducted is located in Section 14.2. Addition safety endpoints such as adverse events, slit lamp findings and lens fitting characteristics may also be descriptive summarized and provided.

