14.2. Sample Size Justification

Phase I of this study was not powered to test non-inferiority of O1D relative to P1 with respect to the primary endpoints. However, data collected during Phase I of the study will be used to power Phase II to test for superiority of the O1D relative to P1 with respect to *Overall comfort*,

Clinical Study Protocol

Johnson & Johnson Vision Care, Inc.

Comfort at the End of the Day and Dryness at the End of the Day. Based on these results from testing for non-inferiority for each primary endpoint from the interim analysis (Phase I analysis), the sample size will be calculated to test all three primary hypotheses for superiority with at least 80% power. This will be calculated using an approximation of the power of an F-test derived from the non-centrality parameter calculated from the observed F-statistic from the generalized linear model described in Section 14.5 for Phase I.⁹ If the sample size calculation for Phase II exceeds 300 then the Sponsor reserves the right to terminate the study. Alpha will be adjusted as described in Section 14.4. Complete details of the sample size calculation for Phase II are described in Section 14.5.

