14.5. Primary Analysis

Phase I (Interim Analysis)

Overall comfort, Comfort at the end of the day, and Dryness at the end of the day

Clinical Study Protocol

Johnson & Johnson Vision Care, Inc.

Subjective responses to each primary endpoint will be grouped as: $aval=1$ is a subject responds' 'Excellent' or 'Very Good', $aval=2$ is a subject responds' 'Good' and $aval=3$ if a subject responds' 'Fair' or 'Poor'. $aval$ will be analyzed separately for each primary endpoint using a generalized linear model with a multinomial distribution and the general logit as the link function. In each model, sequence of lens wear, period, lens type and site id will be included as fixed effects. Prior to fitting the final models for the primary endpoints, allocation of subjects' completion between sites will be evaluated. If a difference of more than 30% is observed between sites, a likelihood ratio test for homogeneous variance will be conducted using a generalized linear mixed model with a multinomial distribution and the general logit as the link function. Comparisons between O1D and P1 will be carried out under the final model using 1-sided 97.5% confidence intervals (CIs) constructed for the odds ratio (O1D over P1).

The Model:

Let $aval_{ijkl} = (aval1_{ijkl}, aval2_{ijkl}, aval3_{ijkl})$ denote the rating for l^{th} subject at the m^{th} site assigned to the k^{th} sequence for the i^{th} study lens during the j^{th} study period ($i=1, 2$; $j=1, 2$; $k=1, 2$; $l=1, \dots, n_m$; $m=1, \dots, 10$). Possible values of $aval_{ijkl}$ are $aval_{ijkl}=1$ if a subject responds: 'Excellent' or 'Very Good', $aval_{ijkl}=2$ if a subject responds: 'Good' and $aval_{ijkl}=3$ if a subject responds: 'Fair' or 'Poor'. The Likelihood will be constructed as follows:

$$\begin{aligned}aval_{ijkl} &\sim \text{Multinomial}(p1_{ijkl}, p2_{ijkl}, p3_{ijkl}) \\p1_{ijkl} &= aval1_{ijkl} \\p2_{ijkl} &= aval2_{ijkl} - aval1_{ijkl} \\p3_{ijkl} &= 1 - \sum_{X=1,2} pX_{ijkl}\end{aligned}$$

$$\text{Logit}(avalX_{ijkl}) = \beta_0 + \beta_1 * sequence_k + \beta_2 * period_j + \beta_3 * lens_{i[j,k]} + \beta_4 * Site_m$$

Where, β_0 is the intercept for $X=1, 2, 3$; $sequence_k=1$ if O1D/P1 and $sequence_k=0$ if P1/O1D; $period_j=1$ if first period and $period_j=0$ if second period; $lens_{i[j,k]}=1$ if O1D and $lens_{i[j,k]}=0$ if P1.

Hypothesis Testing

Hypothesis testing will be conducted separately for each primary endpoint as follows:

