$$\begin{aligned}H_0: OR &\leq 0.67 \\H_a: OR &> 0.67\end{aligned}$$

Where, the OR represents the odds of having a more positive experience (Excellent or Very Good) while wearing O1D compared to P1. Non-inferiority of O1D relative to P1 will be concluded if the lower limit of the 97.5% CI is above 0.67 (using 10% as non-inferiority margin and assuming a reference proportion of 0.5).

Clinical Study Protocol

Johnson & Johnson Vision Care, Inc.

Sample size Estimation for Phase II

If non-inferiority is demonstrated for the primary endpoints, the sample size required to test superiority for each primary endpoint will be estimated. The odds ratio and the cumulative log-odds from the model described above for each endpoint will be used to create a new dataset with the same structure and design as Phase I. This new dataset will then be analyzed using the same model. The statistical power of each endpoint will be calculated using the F-statistics as $\text{Power} = P(F[F_{\text{crit}}, v, ncp] > F_{\text{crit}})$; where F_{crit} is the critical value of the central F distribution ($F_{\text{crit}} = F_{\text{numdf}, \text{dmdf}, 0, \alpha}$) under H_0 (H_0 : centrality param = 0), v is the magnitude of the departure from H_0 and ncp is the non-centrality parameter (Stroup).⁹

Phase II

Overall comfort, Comfort at the end of the day, and Dryness at the end of the day

Subjective responses to each primary endpoint will be grouped as: $aval=1$ is a subject responds' 'Excellent' or 'Very Good', $aval=2$ is a subject responds' 'Good' and $aval=3$ if a subject responds' 'Fair' or 'Poor'. $Aval$ will be analyzed separately for each primary endpoint using a generalized linear mixed model with a multinomial distribution and the cumulative logit as the link function. In each model, sequence of lens wear, period and lens type will be included as fixed effects. Site and subject nested within site will be included as a random effect. Errors between measurements within the same subject across study periods will be modeled using an unstructured covariance (UN) structure. Comparisons between O1D and P1 will be carried out using 1-sided 97.5% confidence intervals (CIs) constructed for the odds ratio (O1D over P1). Superiority of O1D relative to P1 will be concluded if the lower limit of the 97.5% CI is above 1.

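### The 80% power that Section 14.8 states for all three primary hypotheses is computed endpoint by endpoint in Section 14.5, so joint power of 80% is not assured

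*Combined protocol and SAP*

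**What the plan says.** All references are to the combined protocol and SAP.

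- **Section 14.8** describes the purpose of the interim calculation as finding the number of subjects "required to complete Phase II to achieve all primary hypotheses with at least 80% power". It caps Phase II at 300 subjects and lists a required sample size that is too large as a reason to stop.
- **Section 14.2** puts the target less sharply: "the sample size will be calculated to test all three primary hypotheses for superiority with at least 80% power". It adds that alpha will be adjusted as in Section 14.4, and then says "Complete details of the sample size calculation for Phase II are described in Section 14.5".
- **Section 14.5**, under the Phase II sample size estimation, says that "the sample size required to test superiority for each primary endpoint will be estimated". It continues: "The statistical power of each endpoint will be calculated using the F-statistics as", followed by a noncentral F expression. No later step combines the endpoints.
- **Models in Section 14.5.** For Phase I: "In each model, sequence of lens wear, period, lens type and site id will be included as fixed effects", with no subject term listed. The dataset built for sizing reuses that model: "This new dataset will then be analyzed using the same model". The Phase II test model differs: "Site and subject nested within site will be included as a random effect".
- **Decision rule.** Each primary endpoint in Phase II is judged by whether the lower limit of a 1-sided 97.5% interval for the odds ratio exceeds 1 (Section 14.5). Section 14.4 gives 1.67% per hypothesis and does not state its sidedness. Sections 2.3 and 14.4 require all three primary hypotheses to be met before any secondary hypothesis is tested.

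**The concern.** The quantity stated and the quantity computed are different. Achieving all primary hypotheses with 80% power means that the three lower limits exceed 1 together with probability 0.80. Section 14.5 delivers 0.80 for each endpoint taken alone. Unless the three test statistics are perfectly correlated, or two endpoints have far more power than the third, the first probability is smaller than the second.

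The joint probability is the one that decides whether secondary testing opens. The N from this calculation also feeds the decision to run Phase II within the cap of 300. A sponsor reading Section 14.8 would take 80% as the chance that the whole primary set succeeds, and the plan does not calculate that chance. Type I error and bias are not affected.

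**Working it through.** **What can be reproduced.** 0.05/3 = 0.0167 matches the 1.67% of Section 14.4. The 80% itself cannot be recomputed, because the documents give no Phase II N, odds ratio, response distribution or correlation. No printed figure is miscalculated.

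**Inputs.** From the documents: three primary endpoints, a power target of 0.80, a decision at one-sided 2.5% (critical value 1.960), and a nominal 1.67% per hypothesis. Assumed: between-endpoint correlation of the test statistics, rho, from 0.5 to 0.9 and equal for each pair. That range is plausible because the same subjects rate all three items at the same follow-up visit (Section 2.2). Also assumed: normal test statistics and a within-subject correlation r across the two lenses.

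**Step 1: bounds with matched alpha and model.** Joint power cannot exceed the smallest per-endpoint power. If N is the largest of the three sample sizes, that is about 0.80. For three endpoints at 0.80, the lower bound under any dependence is 3 × 0.80 − 2 = 0.40, and independence gives 0.80³ = 0.512.

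**Step 2: joint power with matched alpha and model.** With per-endpoint powers p1, p2, p3 and common correlation rho, joint power is the integral over x of φ(x) × Π Φ((z(pi) − √rho·x)/√(1 − rho)), where z(p) is the standard normal quantile of p.

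| Per-endpoint power | rho 0.5 | 0.7 | 0.8 | 0.9 |
|---|---|---|---|---|
| 80/80/80% | 0.611 | 0.659 | 0.687 | 0.722 |
| 80/90/95% | 0.736 | 0.762 | 0.776 | 0.791 |
| 80/95/99% | 0.777 | 0.789 | 0.794 | 0.799 |

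**Step 3: size at 1.67%, judge by the 1-sided 97.5% interval.** Power of each endpoint at the decision is Φ(z_size + 0.842 − 1.960), where z_size is the critical value used at sizing and 0.842 is z(0.80).

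- 1.67% one-sided: z_size = 2.128, so Φ(1.010) = 0.844 per endpoint.
- 1.67% two-sided (the natural reading of an F-test if it has one numerator degree of freedom): z_size = 2.394, so Φ(1.276) = 0.899 per endpoint.

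| Three equal endpoints | rho 0.5 | 0.7 | 0.8 | 0.9 |
|---|---|---|---|---|
| Sized at 1.67% one-sided | 0.682 | 0.722 | 0.746 | 0.776 |
| Sized at 1.67% two-sided | 0.780 | 0.809 | 0.826 | 0.849 |

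**Step 4: subject effect at test but not at sizing.** As an approximation, the noncentrality at the test is the sizing value times 1/√(1 − r). With matched alpha the sizing value is 1.960 + 0.842 = 2.802. At r = 0.2 it becomes 2.802/√0.8 = 3.132, and per-endpoint power is Φ(3.132 − 1.960) = 0.880.

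| Equal endpoints, matched alpha | rho 0.5 | 0.7 | 0.8 | 0.9 |
|---|---|---|---|---|
| r = 0.1 | 0.675 | 0.716 | 0.740 | 0.771 |
| r = 0.2 | 0.744 | 0.777 | 0.797 | 0.823 |
| r = 0.3 | 0.815 | 0.840 | 0.855 | 0.874 |
| r at which joint power is 0.80 | 0.279 | 0.237 | 0.205 | 0.156 |

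Steps 3 and 4 both push joint power up, and they combine. Sized at 1.67% two-sided with r = 0.1, the equal-endpoint figures are 0.833 to 0.887.

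**The case against.** The strongest reply is that the low figures do not follow the plan's own sizing rule. Section 14.2 says alpha is adjusted as in Section 14.4, so N is set at 1.67%, while success is judged at one-sided 2.5%. If the 1.67% is two-sided, joint power for equal endpoints is already 78% to 85%, and a modest within-subject correlation removes what shortfall remains. This stands as an answer to any fixed number. It rests, however, on an alpha mismatch that is itself an inconsistency. If that were harmonised without changing the power step, the figures of Step 2 would return, subject to the offset in Step 4.

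Two stronger readings are tempting, and the documents do not support either. A reader might infer that Phase II is underpowered at about 61%. That needs matched alpha, no benefit from the subject effect, three equally powered endpoints and a correlation near 0.5, none of which the documents establish. A reader might also infer that the plan leaves open how three sample sizes become one N. Section 14.2 speaks of a single sample size for all three hypotheses, which naturally means the largest of the three. Writing that down is a clarification, and it still secures only the weakest endpoint.

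It can also be said that per-endpoint power is a legitimate target, since a Bonferroni split suits individual claims, and that Section 14.8 is loose shorthand. That is a fair reading of Sections 14.2 and 14.5, but Section 14.8 does not say it. The stand-alone SAP promised in Section 14.1 could add a joint step, yet Section 14.2 places the complete details in Section 14.5.

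**Conclusion.** The concern holds as a mismatch between a stated joint power and a computed per-endpoint power. Joint power of at least 80% is not assured. Neither the size nor the direction of the error is established.

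For three equally powered endpoints, with assumed rho 0.5 to 0.9 and no gain from the subject effect, joint power is about 61% to 72% with matched alpha, 68% to 78% with one-sided 1.67% sizing, and 78% to 85% with two-sided 1.67% sizing. Unequal endpoints narrow the gap: at 80/95/99% with matched alpha, joint power is 78% to 80%. A positive within-subject correlation modelled only in Phase II raises all of these. The figures rest on a normal approximation, a common correlation, and values of rho and r that are assumed. The point is minor: it affects what the sponsor believes about the chance of success when deciding on Phase II.

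**What to change.** 1. In Sections 14.2 and 14.8, state the target as at least 80% power for each primary endpoint.
2. In Section 14.5, confirm that the Phase II N is the largest of the three endpoint sample sizes.
3. Size with the same model (including the subject effect), alpha and sidedness as the Phase II decision interval.
4. At the interim, report beside N the probability that all three lower limits exceed 1. Simulate it from the Phase I estimates under the Phase II model, with the between-endpoint correlation observed in the Phase I subjects.

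The cost is a few wording changes, a little programming, and a stated figure that is less favourable than 80% for all three. No extra subjects, visits or data are needed, because Phase I subjects already rate all three items.

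If the sponsor does intend 80% joint power, wording alone will not do. For equal endpoints at one-sided 2.5% for both sizing and test, with the same model at both, each endpoint would need about 91.0% power at rho 0.5 or 86.2% at rho 0.9. By ((1.960 + z(p))/(1.960 + 0.842))², N rises by a factor of about 1.39 or 1.19. A per-endpoint N above about 216 (300/1.386) or 253 (300/1.185) would then exceed the cap.
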